#### **8.1.2. Sensitivity Analysis**

To assess the robustness of the primary analysis results, the same analysis may be repeated on the PPS with observed cases, and FAS with missing data imputed by the LOCF approach.

In addition, if the scheduled injection was skipped at a visit, BCVA measured at the first visit after that visit will be censored. Descriptive summaries will be performed based on the censored dataset to assess the impact of missing injection on the primary analysis results.

### **8.2. Analyses of Secondary Endpoints**

#### **8.2.1. Primary Analysis**

Frequency and percentage of subjects with BCVA improvement of  $\geq 15$  ETDRS letters (3-line gainers); within 15 letters change (stable) and loss of  $\geq 15$  letters from baseline at Week 24 will be provided based on FAS. The differences in proportion between Arm 2 or 3 and Arm 1, as well as the corresponding 95% confidence intervals based on t-test without multiplicity adjustment will be provided. Besides the summary table, bar plot will be performed.

Change from baseline in CST, MV, CRLT, total lesion area, total area of CNV, and GLD of the total lesion area at Week 24 will be summarized descriptively by treatment arms based on observed data. The differences in mean change between Arm 2 or 3 and Arm 1, and the corresponding 95% confidence intervals based on t-test without multiplicity adjustment will be provided. Scores and percent change from baseline will be provided. Plots of measurement and

change from baseline versus analysis visit will also be provided. Frequency and percentage of subjects with ‘ungradable’ data will be provided.

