5. INTRODUCTION

AMD is the leading cause of irreversible vision loss in developed countries. AMD is characterized by extracellular matrix deposits, known as drusen, accumulating between the retinal pigment epithelium and Bruch's membrane. In exudative or wet AMD unwanted blood vessels grow into the macula which leads to hemorrhage and subretinal fluid. In addition, retinal pigment epithelial detachment, retinal tears, fibrovascular scarring and vitreous hemorrhage may occur. The aberrant growth of leaky vessels is the result of local inflammatory responses leading to disruption of the balance of cytokines that control angiogenesis (Lim et al., 2008).

Angiogenesis is a complex and coordinated process of the growth and sprouting of new blood vessels from pre-existing vasculature. Although several angiogenic factors have been identified, VEGF family proteins, their receptors and intracellular signaling molecules appear to be the key mediators of angiogenesis (Kane et al., 2008).

Exciting advances have been made in understanding the pathogenesis of AMD in recent years. Since 2004, several anti-VEGF medications, such as ranibizumab (Lucentis®), pegaptanib (Macugen®) and afibercept (Eylea®) have been approved by the FDA for patients with wet AMD. Although Eylea®, which is the most recently approved anti-VEGF medication for wet AMD, showed more than 95% of the subjects maintained vision defined as losing < 15 ETDRS letters for 12 months, only 30% of subjects gained > 15 ETDRS letters. Moreover, approximately 30% of subjects still showed cystic intraretinal edema and subretinal fluid after 12 months of treatment (Heier et al., 2012). Therefore, anti-VEGF treatment may not represent the only pathway towards anti-angiogenesis. New or novel approaches to inhibit angiogenesis are needed to elicit further improvements in visual acuity, macular edema, and quality of life in wet AMD patients.

Endoglin (also known as CD105) is a member of the TGF- β receptor family that is expressed by proliferating endothelial cells and is considered as one of the essential factors for angiogenesis. Normal levels of endoglin are needed for endothelial cell proliferation (Guo et al., 2004; Warrington et al., 2005). Endoglin expression is increased by cellular hypoxia through the production of hypoxia-inducible factor-1- α (HIF-1- α), and endoglin protects hypoxic cells from apoptosis (Li et al., 2003).

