11. ASSESSMENT OF EFFICACY

11.1. Best Corrected Visual Acuity (BCVA)

BCVA is the primary efficacy variable for this study, and mean change from baseline in BCVA at Week 24 is the primary efficacy endpoint. Proportion of subjects with BCVA Improvement of ≥ 15 letters, <15 letters change (stable) and loss of ≥ 15 letters from baseline at Week 24 are secondary endpoints.

The visual acuity will be recorded using the ETDRS chart and total number of letters at 4 meter and 1 meter will be recorded. If a subject could not read ETDRS chart, Finger Counts, Hand Motion, Light Perception, or No Light Perception will be recorded.

11.2. Central Subfield Thickness (CST), Macular Volume (MV), Central Retinal Lesion Thickness (CRLT)

CST, MV, and CRLT measured by SD-OCT are secondary efficacy variables, and change in CST, MV, and CRLT from baseline at Week 24 are secondary endpoints. All 3 parameters will be measured by the central reading center.

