### 3. STUDY DESIGN

#### 3.1. General Study Design

This is a randomized, double masked and active controlled study assessing the safety and efficacy of repeated intravitreal injections of DE-122 (2.0 mg or 4.0 mg) in combination with Lucentis® compared to Lucentis® monotherapy in subjects with wet AMD. Seventy-six (76) subjects with wet AMD were randomly assigned to one of three treatment arms in two stages:

[figure not shown]
- Arm 1: Sham + Lucentis® 0.5 mg (N=17)
- Arm 2: DE-122, 2.0 mg + Lucentis® 0.5 mg (N=31)
- Arm 3: DE-122, 4.0 mg + Lucentis® 0.5 mg (N=28)

As shown in the Study Design Diagram ([Figure 1](#)), this study will consist of two stages. In Stage 1, the first 6 subjects will be randomized to either Arm 1 or Arm 2 in a 1:1 ratio. After all the 6 subjects have completed the Week 4 visit, the Safety Review Team will review the data to determine whether or not the safety and tolerability is acceptable. Subsequently in Stage 2, approximately 70 subjects will be randomized in a 1:2:2 ratios among the three arms.

Subjects will receive, in combination with Lucentis®, either 6 monthly intravitreal injections of DE-122 (2.0 mg), DE-122 (4.0 mg), or Sham in the study eye. The Primary Analysis is planned when all subjects complete the Week 24 visit. The Follow-up Analysis is planned at Week 32 to assess the number of anti-VEGF injections used for Rescue in addition to efficacy and safety data.

To be eligible, a subject must have been previously treated (i.e., At least 3 IVT injections of Anti-VEGF for treatment naïve eyes or eyes adequately maintained on continuous intravitreal anti-VEGF therapy). This condition was not required for subjects who enrolled before Protocol Amendment 06.

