### **3.3. Sample Size Planning**

Approximately 76 subjects (Arm 1: 17, Arm 2: 31, Arm 3: 28) with wet AMD will be enrolled at approximately 14 sites. The sample size is not based upon any statistical considerations.

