#### **6.5. Multiple Comparisons / Multiplicity**

Multiplicity adjustment is not applicable to this study.

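### t-based 95% intervals for the BCVA category proportions break down for ≥15-letter loss: with no events in two compared arms the interval is [0, 0]

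*SAP*

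**What the plan says.** Protocol 11.1 splits BCVA change into a gain of at least 15 letters, a change of less than 15 letters, and a loss of at least 15 letters, and states that the proportions "from baseline at Week 24 are secondary endpoints". SAP 8.2.1 gives the frequency and percentage in each category and adds "The differences in proportion between Arm 2 or 3 and Arm 1, as well as the corresponding 95% confidence intervals based on t-test". No correction is made for the number of comparisons. The same t-based wording is used for the continuous endpoints.

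The rule covers all three categories. Neither SAP 8.2.1 nor the general rules in SAP section 6 say what happens when a category has few or no events. The SAP also does not say whether the t-interval uses a pooled variance or the Welch form.

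Planned arm sizes are in SAP 3.3: "Arm 1: 17, Arm 2: 31, Arm 3: 28". The documents give no expected loss rate for this trial. The nearest figures are background on another anti-VEGF drug in Protocol section 5. On loss, it reports that "more than 95% of the subjects maintained vision defined as losing < 15 ETDRS letters for 12 months". On gain, the figure it gives is that "only 30% of subjects gained > 15 ETDRS letters".

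**The concern.** A t-interval for a difference in proportions takes its width from the observed variance of 0/1 data. If neither arm has an event, that variance is zero and the interval shrinks to a single point. If only one arm has no events, that arm adds no variance of its own. Under Welch its term drops out. Under pooling it borrows from a pooled variance that its own zeros have reduced. In both cases the interval is narrower than the data justify.

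This matters for rare categories, chiefly loss of at least 15 letters. The study tests no hypothesis, so the estimate and its interval are the whole between-arm comparison of serious vision loss. An interval of [0, 0] tells the reader that only a zero difference fits the data, although 17 and 31 event-free subjects leave wide uncertainty.

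The concern does not extend to gain of at least 15 letters. The only gain rate in the documents is about 30%. Prior treatment, which might limit gains, was also not universal: "This condition was not required for subjects who enrolled before Protocol Amendment 06" (SAP 3.1).

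**Working it through.** **Arm sizes.** Stage 1 assigns 6 subjects 1:1 to Arms 1 and 2 (3 + 3). Stage 2 assigns 70 subjects 1:2:2 (14 + 28 + 28). This gives 3 + 14 = 17, 3 + 28 = 31 and 28, total 76, as stated.

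**Expected losses.** At 5%, the top of the background range, the expected counts are 17 × 0.05 = 0.85, 31 × 0.05 = 1.55 and 28 × 0.05 = 1.4. All true rates below are assumptions. Differences are DE-122 arm minus Arm 1.

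**Interval formulas.** For x events in n subjects, p = x/n and s² = n·p(1−p)/(n−1).
- Pooled: SE² = [((n₁−1)s₁² + (n₂−1)s₂²)/(n₁+n₂−2)]·(1/n₁+1/n₂).
- Welch: SE² = s₁²/n₁ + s₂²/n₂.
- Newcombe: combines the Wilson limits of the two arms. For x = 0 the Wilson upper limit is z²/(n+z²), with z² = 3.84.

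**No events in either arm.** Both s² are 0, so pooled and Welch both give [0, 0]. The Wilson upper limits are 3.84/20.84 = 18.4% (n = 17), 3.84/34.84 = 11.0% (n = 31) and 3.84/31.84 = 12.1% (n = 28). Newcombe is therefore [-18.4, +11.0] points for Arm 2 v Arm 1 and [-18.4, +12.1] for Arm 3 v Arm 1. Miettinen-Nurminen gives [-18.8, +11.2] and [-18.8, +12.3].

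**One event, in Arm 2 only (0/17 v 1/31).** The difference is 3.2 points and s₂² = 31 × (1/31)(30/31)/30 = 0.0323.
- Pooled: SE = √[(30 × 0.0323/46)(1/17 + 1/31)] = 0.0438; interval [-5.6, +12.0].
- Welch: SE = √(0.0323/31) = 0.0323 on 30 df; interval [-3.4, +9.8].
- Newcombe: [-15.4, +16.2].

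**Chance of a zero-width interval.** At a common true rate p this is (1−p)^48 for Arm 2 v Arm 1 and (1−p)^45 for Arm 3 v Arm 1. For at least one of the two it is (1−p)^48 + (1−p)^45 − (1−p)^76.

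| Common loss rate | Arm 2 v Arm 1 | Arm 3 v Arm 1 | At least one |
|---|---|---|---|
| 2% | 37.9% | 40.3% | 56.7% |
| 3% | 23.2% | 25.4% | 38.7% |
| 5% | 8.5% | 9.9% | 16.4% |
| 10% | 0.6% | 0.9% | 1.5% |

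**Coverage of the nominal 95% interval.** For each pair of true rates, the binomial probabilities of all (x₁, x₂) whose interval contains the true difference are summed.

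| True rate, Arm 1 / DE-122 arm | Arm 2 v 1: pooled / Welch / Newcombe | Arm 3 v 1: pooled / Welch |
|---|---|---|
| 2% / 5% | 79.4 / 85.2 / 98.9 | 82.0 / 82.9 |
| 3% / 6% | 84.9 / 90.4 / 98.2 | 87.7 / 88.9 |
| 5% / 2% | 74.9 / 72.3 / 99.5 | 75.7 / 75.4 |
| 10% / 5% | 92.9 / 82.7 / 97.1 | 90.4 / 82.5 |
| 5% / 5% | 98.6 / 97.0 / 98.6 | 98.4 / 97.7 |
| 2% / 10% | 95.5 / 95.4 / 98.2 | 93.9 / 94.3 |
| 30% / 30% | 95.3 / 95.1 / 95.3 | 94.5 / 95.0 |

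**Whole-percent grid, 1% to 30% in each arm.** With both rates from 1% to 5% and unequal, all 20 combinations cover below 90%, for both t-forms and both comparisons. With both rates from 10% to 30%, none does (minimum 90.1%). Newcombe's minimum over the whole grid is 94.6% (17 v 31) and 94.4% (17 v 28).

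**The case against.** The best counter-argument is about weight. Protocol 16.2.2 defines no hypothesis, and Protocol 16.6.2 asks only that these proportions be summarized and tabulated; the interval is an addition in the SAP. No decision depends on it. Counts and percentages stand beside it, so few readers who see 0/17 and 0/31 would take [0, 0] literally. Mean BCVA change has its own interval, which is unaffected. All of this stands, and it is why the point is a recommended correction and no more.

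The coverage figures also need context. At equal rates the t-interval over-covers, though partly because [0, 0] happens to contain the true value of zero. The lowest coverage on the grid, about 48% for 17 v 31, is at 2% v 1%, where the true difference is one point and the chance of no events at all is 0.98^17 × 0.99^31 = 52%. At 2% v 10% coverage is close to nominal. Larger differences are not always safe, however: with 10% in Arm 1 and 5% in a DE-122 arm, Welch covers about 83%.

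The loss-rate anchor is weak: a different drug, 12 months instead of 24 weeks, and no trial-specific figure. At a common 10% the collapse is very unlikely. Some software may also print a missing value instead of [0, 0]. That would be less misleading, but still no usable interval, and the plan does not provide for it.

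**Conclusion.** The concern holds. With no events in both compared arms the planned method gives a zero-width interval by construction, and the SAP has no fallback. How likely this is depends on the unknown loss rate. At common rates of 2% to 5% the chance is 38% down to 8.5% for Arm 2 v Arm 1 and 40% down to 9.9% for Arm 3 v Arm 1; at 10% it is below 1% for each. When both rates are between 1% and 5% and differ, coverage is below 90% throughout.

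These figures assume that all 17, 31 and 28 subjects have a Week 24 value. Fewer evaluable subjects would make the collapse more likely. The fault is confined to rare categories, and its effect is misleading precision in a descriptive secondary table. For outcomes near 30%, and for the continuous endpoints, the t-based intervals raise no such concern.

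**What to change.** In SAP 8.2.1, for the three BCVA category proportions only, replace the t-test basis with Newcombe hybrid-score 95% confidence intervals for the risk difference. Miettinen-Nurminen intervals would serve equally well and give nearly the same limits here, but the SAP should name one method. Use it for all three categories, so that the method does not depend on the observed counts. Leave the t-based intervals for the continuous endpoints as they are.

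The cost is one phrase, with no new data and no design change. When events are rare the intervals will be wider and somewhat conservative (Newcombe covers 98.2% to 99.5% in the cases 2% v 5%, 3% v 6% and 5% v 2%). For outcomes near 30%, coverage is essentially unchanged.

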### **8.2.2. Sensitivity Analysis**

To assess the robustness of the primary analysis results, the same analysis may be repeated on the PPS with observed cases.

In addition, if the scheduled injection was skipped at a visit, the efficacy data measured at the first visit after that visit will be censored. Descriptive summaries will be performed based on the censored dataset to assess the impact of missing injection on the primary analysis results.

### **8.3. Subgroup Analyses**

To assess the homogeneity of treatment effects among subgroups, primary endpoint will be analyzed for the following subgroups:

- Age group (< 65, or  $\geq$  65 years)
- Sex (males or females)
- Country (Philippine or US)
- Lesion type (PCV or non-PCV)
- Prior anti-VEGF treatment in the study eye (yes or no)
- Type of most recent prior anti-VEGF treatment in the study eye (type 1: Lucentis or Ranibizumab; type 2: Avastin or Bevacizumab; type 3: Eylea or Aflibercept)
- Protocol version (before or on/after Amendment 06)
- Lens status (phakic or non- phakic).

Other subgroup analyses may be performed as suggested by the data.

## **9. SAFETY ANALYSES**

The safety-related measures collected in this study include AEs, IOP, slit-lamp biomicroscopy variables, indirect ophthalmoscopy variables, laboratory tests (hematology, chemistry, and urinalysis), vital signs, physical exam, fundus photography, fluorescein angiography, EKG, and pregnancy.

The Safety population will be used for all safety summaries, where subjects will be classified by actual treatment received.

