12.2. Safety Parameters

The safety assessments will include AEs, slit lamp biomicroscopy, indirect ophthalmoscopy, BCVA, IOP, fundus photography, fluorescein angiography, serum chemistry, hematology, urinalysis, vital signs, physical examination, EKG, and pregnancy.

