16.7. Safety Analysis

All safety outcome measures will be summarized descriptively for the Safety Population. The safety outcome measures include adverse events (AEs), BCVA, slit-lamp biomicroscopy, indirect ophthalmoscopy, intraocular pressure (IOP), serum chemistry, hematology, urinalysis, vital signs, physical examination, fundus photography, fluorescein angiography, EKG and pregnancy.

AEs will be coded using the Medical Dictionary for Regulatory Activities (MedDRA).

Subjects with any AEs will be tabulated by system organ classification and preferred term specified in the MedDRA. Similarly, subjects with any ocular and non-ocular AEs and ESIs will be tabulated separately. AEs, ocular and non-ocular, as well as ESIs will also be summarized by relationship to treatment and maximum severity. In addition, SAEs and discontinuations due to AEs will be summarized.

Ocular safety outcome measures will be summarized using descriptive statistics.

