#### **2.2.3. Safety Endpoint**

The safety of DE-122 will be evaluated by:

- Adverse events (AEs)
- Slit lamp biomicroscopy
- IOP
- Indirect ophthalmoscopy

- Laboratory assessment including serum chemistry, hematology, and urinalysis
- Vital signs
- Electrocardiogram (EKG)

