## **8. EFFICACY ANALYSES**

Unless specified otherwise, the efficacy analyses will be performed on the FAS, where subjects are classified by planned treatment, irrespective of the actual treatment received.

Unless specified otherwise, all efficacy analyses will be performed on the study eye, and the data on fellow eye will not be used.

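### The SAP omits the BCVA safety summary that the protocol requires, so letter loss is counted from BCVA data only at Week 24

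*SAP*

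**What the plan says.** **Protocol.** Section 12.2 names BCVA as a safety parameter: "The safety assessments will include AEs, slit lamp biomicroscopy, indirect ophthalmoscopy, BCVA, IOP, fundus photography, fluorescein angiography". Section 16.1.1 includes it in the Week 24 safety assessments. Section 16.7 states that "All safety outcome measures will be summarized descriptively for the Safety Population" and then: "The safety outcome measures include adverse events (AEs), BCVA, slit-lamp biomicroscopy, indirect ophthalmoscopy, intraocular pressure (IOP), serum chemistry". Section 12.1.2 makes a loss of 30 or more letters from baseline a sight-threatening, and hence serious, event in either eye.

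**SAP.** Section 2.2.3 opens its list with "The safety of DE-122 will be evaluated by" and does not name BCVA. Table 5 (safety measures) has no BCVA row. Section 9 begins "The safety-related measures collected in this study include AEs, IOP, slit-lamp biomicroscopy variables, indirect ophthalmoscopy variables", completes the list without BCVA, and none of Sections 9.1 to 9.8 deals with it. BCVA appears only under efficacy, where "all efficacy analyses will be performed on the study eye, and the data on fellow eye will not be used" unless otherwise specified. The one letter-loss category is in Section 8.2.1: a loss of 15 or more "letters from baseline at Week 24 will be provided based on FAS".

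**The concern.** Loss of vision is a central ocular harm for a drug injected into the eye. The protocol treats it so: a 30-letter loss is both a serious event (12.1.2) and a Stage 1 safety criterion (7.4.1). SAP Section 1 makes the SAP's analyses the basis of the study report, so a summary that the SAP leaves out may not be produced.

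The efficacy count is a poor substitute because it is tied to one visit. A subject whose vision falls and who then leaves has no Week 24 value. If poor vision is a reason for leaving, the count misses the subjects of most interest. The reader of the report would then depend on event reporting for a harm that could be read directly from the letter scores.

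**Working it through.** **1. Compare the lists.** Protocol 16.7 names 14 safety measures: AEs, BCVA, slit lamp, indirect ophthalmoscopy, IOP, chemistry, haematology, urinalysis, vital signs, physical examination, fundus photography, angiography, EKG and pregnancy. The opening list of SAP Section 9 contains 13 of these. BCVA is the only one missing, and no reason is given.

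**2. Where letter loss is counted.** SAP Table 3 has nine post-baseline analysis visits: Weeks 1, 4, 8, 12, 16, 20, 24, 28 and 32. A letter-loss category is planned at one, Week 24. Six visits precede it and two follow it, so 9 − 1 = 8 have no count. There is no 30-letter category at any visit. SAP 6.2 allows LOCF in general for efficacy measures. SAP 8.2.2, however, plans only a per-protocol repeat on observed cases and a censoring analysis for skipped injections; it gives no LOCF version of the loss category.

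**3. Follow one subject (illustration).** Suppose a subject has lost 30 letters and exits on Day 60.
- Protocol 8.3 asks for the exit assessments, which include BCVA, on the day of discontinuation where possible.
- SAP Table 3 assigns Day 60 to Week 8 (window 44 to 71). The Week 24 window is 156 to 183, so there is no Week 24 value and the subject is not among the losers.
- By 12.1.2 the event is an SAE. It enters the Safety Population tables and listings of SAP 9.1 if the investigator marks it serious (SAP 4.3.1.2).
- The value also enters by-visit BCVA displays (Protocol 16.6.1, SAP 8.1.1). With all subjects observed, and against no change, one 30-letter loss moves an arm mean by 30/17 = 1.8, 30/31 = 1.0 or 30/28 = 1.1 letters. The minimum in a by-visit summary could show it, but not how many subjects were affected.

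Change the loss to 20 letters and the SAE letter definition is not met. The event is then recorded only if the investigator reports it. Protocol 12.1.1 excludes lack of efficacy as an AE unless a clinically significant change is assessed.

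**4. Two further filters.** When several values fall in one analysis window, SAP 4.1.5 keeps the one from an injection visit, so a poor unscheduled reading can drop out of by-visit summaries. SAP 8.1.1 censors BCVA after rescue at Weeks 28 and 32, and a fall of 5 or more letters is itself a rescue criterion (SAP 4.3.3).

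**5. Size.** The planned arm sizes reproduce:
- Stage 1: 6 subjects at 1:1 give 3, 3 and 0.
- Stage 2: 70 subjects at 1:2:2 give 14, 28 and 28.
- Total: 17 + 31 + 28 = 76.

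One uncounted case is 1/17 = 5.9%, 1/31 = 3.2% or 1/28 = 3.6% of an arm. These figures show only how far one case shifts a rate.

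**The case against.** The strongest reply is that severe loss is already covered. A 30-letter loss is an SAE. SAP 9.1 tabulates SAEs on the Safety Population by actual treatment for the on-treatment period, the follow-up period and the entire study, with ocular SAEs shown separately for study and fellow eyes. It also lists SAEs and AEs leading to discontinuation. Beyond that, the protocol plans observed and LOCF BCVA by visit, the SAP permits an LOCF repeat of mean change, and study parameters are listed. A reader might therefore infer from the omission that early severe loss appears in no planned output. The documents do not support that inference.

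Other parts of the reply also stand:
- Any Safety Population subject with a post-baseline study-eye BCVA is already in the FAS, so changing population adds no study-eye data. It changes only classification, from as randomised to as treated.
- The fellow-eye exclusion is confined to efficacy analyses, and no protocol text requires a fellow-eye BCVA table.
- The Stage 1 criterion is applied by the Safety Review Team at Week 4, independently of the SAP tables.
- Protocol 16.7 asks only for descriptive summaries. The letter thresholds proposed below are a recommendation, not a protocol requirement.

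The reply does not supply a count taken from the data. SAE status rests on an investigator's answer, the LOCF repeat is optional in the SAP and concerns mean change, and losses of 15 to 29 letters fall below the SAE letter definition. Nor does the SAP rely on event reports alone elsewhere. A 10 mmHg IOP rise at 60 minutes is a reportable AE, yet SAP 9.4 also lists those subjects from the measurements.

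**Conclusion.** The protocol and SAP disagree, and the SAP should be corrected. As written, letter loss is counted from BCVA data only at Week 24, at the 15-letter threshold, in the study eye, in the FAS, with no LOCF version. At other times, and in subjects who leave before the Week 24 window, loss is captured only through investigator-reported events, by-visit displays and an optional LOCF analysis of mean change. The gap matters most for losses of 15 to 29 letters and for larger losses not reported as serious.

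How many subjects this would affect cannot be computed, because the documents give no rate of vision loss or of withdrawal. It would be tempting to treat a shift of 3.2 to 5.9 percentage points as comparable with the true rate of severe loss, but nothing in the documents supports that. The conclusion assumes that the SAP's sections list the analyses intended. It does not affect the primary efficacy analysis.

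**What to change.** Add BCVA to SAP 2.2.3, Table 5 and Section 9, with a short subsection. For the Safety Population by actual treatment, provide:
- change from baseline in BCVA by visit;
- the number and percent of subjects with a study-eye loss of 15 or more, and of 30 or more, letters from baseline at any post-baseline visit, by the analysis periods in SAP Table 2;
- a listing of these subjects, to which fellow-eye results can be added.

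The any-visit counts should use every recorded value, including unscheduled and early-exit visits, and not only the one selected per analysis window. State the denominator, and state whether values after rescue are included. If leaving BCVA out was deliberate, the SAP should say so and give the reason. The cost is one table and one listing from data already collected.
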